8.2 Study Assessments

8.2.1 Self-Report Questionnaires

- The Aphasia Communication Outcome Measure (ACOM): A measurement of patient-reported communicative functioning in aphasia⁷³.
- Stroke and Aphasia Quality of Life-39 Item (SAQOL-39): A measurement of quality of life among individuals with aphasia⁷⁴.
- Patient-Reported Outcomes Measurement Information System (PROMIS) – Social Roles and Activities: A measurement of the perceived ability to perform one’s usual social roles and activities⁷⁵.
- Patient-Reported Outcomes Measurement Information System (PROMIS) - Global Health: A measurement of symptoms, functioning, and healthcare-related quality of life⁷⁵.

8.2.2 Cognitive and PPA symptoms Assessments (Exploratory)

- Trained and Untrained Words: Participants will verbally name pictures of common nouns and verbs with the support of a lexical retrieval cueing hierarchy aimed at facilitating word retrieval through self-cueing³⁵.
- Quick Aphasia Battery- (QAB): This aim of the QAB is to provide a reliable and multidimensional assessment of language function in a shorter time period across 8 language subtests ⁷⁶. QAB has been adapted for remote use.
- Boston Naming Test (BNT)-Short form: Consists of 15 line-drawn pictures presented in order of difficulty from “easiest” (e.g., “house”) to “most difficult” (e.g., “palette”). Participants have 20 seconds to name each item correctly with a cueing hierarchy⁷⁷.

- Controlled Oral Word Association Test (COWAT): A measure of verbal (phonemic and semantic) fluency where participants are given 60 seconds to name all of the words within a given category⁷⁸.

8.3 Study Schedule

8.3.1 Pre-Screening

- Conduct eligibility phone screen to assess general eligibility.
- PPA diagnosis and tDCS eligibility determined via medical records and tDCS safety questionnaire
- Eligible participants will be scheduled for a baseline visit.

8.3.2 Consent & Telehealth medical screening

- Remote consent through SendSafe (20 minutes)
Once consented, study personnel will send tDCS and study materials to participant

8.3.3 Baseline Visit (visit 1)

- Baseline language assessment (1.5 hours)
- Self-report questionnaires (20 minutes)

8.3.4 tDCS Session 1 (Visit 2)

- Train participant to use tDCS device (20 minutes)
- Perform tDCS tolerability test (2 minutes)
- Complete first remotely-supervised tDCS session + language skills practice (45 minutes)

8.3.5 Remotely-Supervised tDCS sessions 2-19 (Visits 3-20)

- 20x30 minutes of active tDCS with simultaneous language skills practice (45 minutes)
- AE reporting

8.3.6 tDCS Session 20 & Treatment-end Visit (Visit 21)

- Participants will complete tDCS and word naming practice session 20 (45 minutes)
- Post-stimulation language assessment (1.5 hours)
Equipment return

9 Assessment of Safety

9.1 Definition of Adverse Events (AE)

An **adverse event** (AE) is any symptom, sign, illness or experience that develops or worsens in severity during the course of the study. Intercurrent illnesses or injuries should be regarded as adverse events. Abnormal results of diagnostic procedures are considered to be adverse events if the abnormality:

- results in study withdrawal
- is associated with a serious adverse event
- is associated with clinical signs or symptoms
- leads to additional treatment or to further diagnostic tests
- is considered by the investigator to be of clinical significance

9.1.1 Definition of Serious Adverse Events (SAE)

Serious Adverse Event

Adverse events are classified as serious or non-serious. A **serious adverse event** is any AE that is:

- fatal
- life-threatening
- requires or prolongs hospital stay
- results in persistent or significant disability or incapacity
- a congenital anomaly or birth defect
- an important medical event

Important medical events are those that may not be immediately life threatening, but are clearly of major clinical significance. They may jeopardize the subject, and may require intervention to prevent one of the other serious outcomes noted above. For example, drug overdose or abuse, a seizure that did not result in in-patient hospitalization, or intensive treatment of bronchospasm in an emergency department would typically be considered serious.

All adverse events that do not meet any of the criteria for serious should be regarded as **non-serious adverse events**.

9.1.2 Definition of Unanticipated Problems (UP)

Unanticipated Problems Involving Risk to Subjects or Others

Any incident, experience, or outcome that meets all of the following criteria:

- Unexpected in nature, severity, or frequency (i.e. not described in study-related documents such as the IRB-approved protocol or consent form)
- Related or possibly related to participation in the research (i.e. possibly related means there is a reasonable possibility that the incident experience, or outcome may have been caused by the procedures involved in the research)
- Suggests that the research places subjects or others at greater risk of harm (including physical, psychological, economic, or social harm).

This definition could include an unanticipated adverse device effect, any serious adverse effect on health or safety or any life-threatening problem or death caused by, or associated with, a device, if that effect, problem, or death was not previously identified in nature, severity, or degree of incidence in the investigational plan or application (including a supplementary plan or application), or any other unanticipated serious problem associated with a device that relates to the rights, safety, or welfare of subjects (21 CFR 812.3(s)).

9.1.3 Reporting of Pregnancy

Women who are pregnant or breastfeeding as determined by participant self-report or medical record will not be included in this study. Women who cannot confirm their pregnancy status via self-report or medical record will be excluded.

9.2 Classification of an Adverse Event

9.2.1 Severity of Event

For AEs not included in the protocol defined grading system, the following guidelines will be used to describe severity.

- **Mild** – Events require minimal or no treatment and do not interfere with the participant's daily activities.
- **Moderate** – Events result in a low level of inconvenience or concern with the therapeutic measures. Moderate events may cause some interference with functioning.
- **Severe** – Events interrupt a participant's usual daily activity and may require systemic drug therapy or other treatment. Severe events are usually potentially life-threatening or incapacitating.

9.2.2 Relationship to Study Agent

The clinician's assessment of an AE's relationship to study device is part of the documentation process, but it is not a factor in determining what is or is not reported in the study. If there is any doubt as to whether a clinical observation is an AE, the event should be reported. All AEs must have their relationship to study agent assessed. In a clinical trial, the study product must always be suspect. To help assess, the following guidelines are used.

- **Related** – *The AE is known to occur with the study agent, there is a reasonable possibility that the study agent caused the AE, or there is a temporal relationship between the study agent and event. Reasonable possibility means that there is evidence to suggest a causal relationship between the study agent and the AE.*

- **Possibly Related** – *The AE may be related to the device. However, other factors may have contributed to the event (e.g., the participant’s clinical condition, other concomitant events). Although an AE may rate only as “possibly related” soon after discovery, it can be flagged as requiring more information and later be upgraded to “probably related” or “definitely related,” as appropriate.*
- **Not Related** – *There is not a reasonable possibility that the administration of the study agent caused the event, there is no temporal relationship between the study agent and event onset, or an alternate etiology has been established.*

9.2.3 Expectedness

[name] will be responsible for determining whether an AE is expected or unexpected. An AE will be considered unexpected if the nature, severity, or frequency of the event is not consistent with the risk information previously described for the study agent.

9.3 Time Period and Frequency for Event Assessment and Follow-Up

The occurrence of an AE or SAE may come to the attention of study personnel during study visits or upon review by a study monitor. All AEs including local and systemic reactions not meeting the criteria for SAEs will be captured on the appropriate RF. Information to be collected includes event description, date of onset, clinician’s assessment of severity, relationship to study product (assessed only by those with the training and authority to make a diagnosis), and time of resolution/stabilization of the event. All AEs occurring while on study must be documented appropriately regardless of relationship. All AEs will be followed to adequate resolution.

Any medical condition that is present at the time that the participant is screened will be considered as baseline and not reported as an AE. However, if the study participant’s condition deteriorates at any time during the study, it will be recorded as an AE. UPs will be recorded in the data collection system throughout the study.

Changes in the severity of an AE will be documented to allow an assessment of the duration of the event at each level of severity to be performed. AEs characterized as intermittent require documentation of onset and duration of each episode.

The PI will record all reportable events with start dates occurring any time after informed consent is obtained until 7 (for non-serious AEs) or 30 days (for SAEs) after the last day of study participation. At each study visit, the investigator will inquire about the occurrence of AE/SAEs since the last visit. Events will be followed for outcome information until resolution or stabilization.

All unresolved adverse events should be followed by the investigator until the events are resolved, the subject is lost to follow-up, or the adverse event is otherwise explained. At the last scheduled visit, the investigator should instruct each subject to report any subsequent event(s) that the subject, or the subject’s personal physician, believes might reasonably be related to participation in this study. The investigator should notify the study sponsor of any death or adverse event occurring at any time after a subject has discontinued or terminated study participation that may reasonably be related to this study. The sponsor should also be notified if the investigator should become aware of the development of cancer or of a congenital anomaly in a subsequently conceived offspring of a subject that has participated in this study.

9.4 Reporting Procedures – Notifying the IRB

9.4.1 Adverse Event Reporting

Adverse event rates will be calculated and reviewed at DSMP meetings. Adverse event rates will be reported to the IRB as described previously. Should adverse event rates exceed the normal rates observed in the literature, the study PI will place the study on hold and review the safety of the study.

9.4.2 Serious Adverse Event Reporting

Serious adverse events that are related to the study device or interventions will be reported to the IRB within 24 hours of becoming aware of the occurrence.

9.4.3 Unanticipated Problem Reporting

Incidents or events that meet the OHRP criteria for UPs require the creation and completion of an UP report form. It is the site investigator's responsibility to report UPs to their IRB and to the study sponsor. The UP report will include the following information:

- Protocol identifying information: protocol title and number, PI's name, and the IRB project number;
- A detailed description of the event, incident, experience, or outcome;
- An explanation of the basis for determining that the event, incident, experience, or outcome represents an UP;
- A description of any changes to the protocol or other corrective actions that have been taken or are proposed in response to the UP.

To satisfy the requirement for prompt reporting, UPs will be reported using the following timeline:

- UPs that are SAEs will be reported to the IRB and to the study sponsor within 5 business days of the investigator becoming aware of the event.
- Any other UP will be reported to the IRB and to the study sponsor within 10 business days of the investigator becoming aware of the problem.
- All UPs should be reported to appropriate institutional officials (as required by an institution's written reporting procedures), the supporting agency head (or designee), and OHRP within 10 business days of the IR's receipt of the report of the problem from the investigator.

The study sponsor is responsible for conducting an evaluation of an unanticipated adverse device effect and shall report the results of such evaluation to FDA and to all reviewing IRBs and participating investigators within 10 working days after the sponsor first receives notice of the effect. Thereafter the sponsor shall submit such additional reports concerning the effect as FDA requests.

9.6 Study Halting Rules

There are no predetermined stopping rules.

9.7 Safety Oversight

9.7.1 Data Safety Monitoring

It is the responsibility of the Principal Investigator to oversee the data safety monitoring of the study at his/her site. Data safety monitoring meetings will occur with every 10th subject enrolled (beginning when first participant is enrolled) and will include careful assessment of research procedures including protocol adherence, regulatory documentation, enrollment (e.g. rate of enrollment, screen fails, withdrawals), unanticipated problems (e.g. device malfunction, connection issues), and any issues that may arise during the course of research. There are no predefined stopping rules.

Meetings will be documented in data safety monitoring reports (DSMR). An annual DSMR will be submitted to the IRB at the time of continuing review. This data safety monitoring will include careful assessment (e.g. frequency, relatedness, and expectancy) and appropriate reporting of adverse events (e.g. skin tingling, itching, warming, irritation) as noted above. Each tDCS administration will occur in the context of a live video visit through Zoom. With this real-time supervision of treatment, risk will be systematically monitored and minimized.

9.7.2 Medical Monitoring

[name], MD, Director of the NYU Langone MSCCC, will serve as medical monitor for this study and will be involved in data safety monitoring. Consistent with her ongoing role for the NYU Langone Health tDCS Program, [name] will be responsible for resolving any clinical matters that may arise (e.g., unanticipated side effects of tDCS), including careful assessment of the number and type of serious adverse events, determining relatedness to the research, and resolution. This will be done through quarterly meetings with [name] to review adverse events. Any adverse event that is judged to be treatment limiting or severe will be immediately addressed by [name] per standard medical care and reported to IRB following guidelines. If these cases do occur, treatment will not resume until [name] gives medical clearance to proceed.

10 Statistical Considerations

10.1 Statistical and Analytical Plans (SAP)

Study data will be collected through REDCap survey function, and these records will be printed and stored in a locked cabinet only accessible to the research staff. While survey data is collected via REDCap, no data will be stored in REDCap. All data will be destroyed from REDCap after it is transferred for storage.

10.2 Statistical Hypotheses

This is a pilot test to assess the feasibility of RS-tDCS with word naming practice. The primary outcome measure will be percent compliance (e.g., at least 16/20 RS-tDCS sessions completed per participant).

In exploratory analyses, pre- and post- language assessment outcomes (trained and untrained words, QAB, BNT, COWAT) will be compared to determine if the intervention led to improved scores. Descriptive analyses will be completed to identify any trends in predicting those participants who are most likely to have improvement in language function at study end (e.g., age, gender, baseline function).

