SD	Standard Deviation
SAE	Serious Adverse Event/Serious Adverse Experience

SOP	Standard Operating Procedure
svPPA	Semantic Variant PPA
tDCS	Transcranial Direct Current Stimulation
US	United States
WAIS-IV	Wechsler Adult Intelligence Scale – 4 th Edition

Protocol Summary

Title	Remotely Supervised Transcranial Direct Current Stimulation (tDCS) for Primary Progressive Aphasia (PPA)
Short Title	RS-tDCS for PPA
Brief Summary	Approximately 30 participants with PPA will be nationally-recruited in an open-label trial of a completely remote intervention to receive four weeks (5 x 30 min daily sessions per week) of active tDCS (2.0 mA, F7: left anodal) paired with simultaneous word naming practice
Objectives	
 - Evaluate the feasibility of RS-tDCS paired with word naming practice in patients with PPA - Collect preliminary efficacy data measured by change in scores on language assessment to support future grant applications
Methodology	Open Label Design
Endpoint	
Primary Endpoints:
 
 - Feasibility judged by study completion percentage. The study will be deemed feasible if participants complete 16/20 RS-tDCS sessions 
Secondary Endpoints:
 
 - language assessment scores (QAB, BNT, COWAT) - The number of trained and untrained language probes identified at treatment end - Self-report questionnaires (ACOM, SAQOL-39, PROMIS Social Roles and Activities, and PROMIS Global Health)
Study Duration	2 years
Participant Duration	Approximately 1 month (4 weeks of intervention)
Duration of IP administration	20x30 minutes daily sessions of IFG tDCS combined with word naming practice
Population	N=30 participants (ages 45-85) diagnosed with early-stage primary progressive aphasia
Study Sites	NYU Langone Health [name]
Number of participants	N=30 participants

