7.1.1 Word Naming Practice

Each tDCS session will include simultaneous word naming practice via live video visit supervision with the trained tDCS clinician. tDCS clinicians for this study will be experienced psychometricians with master's level training and

supervised by speech and language pathologist, [name]. Consistent with the protocol outlined by Flurie et al, 2020, study participants, with caregiver support, will select 100 treatment items of personal relevance (i.e., high familiarity and frequency) from a fixed list of 220 possible items representing everyday objects (nouns) and actions (verbs) (e.g., hat, toothbrush, book, supermarket, coffee, cooking, reading)³³. Unselected items from the original list of 220 items served as the control word naming list. Baseline performance will dictate the number of words reviewed per treatment session to reduce the burden on participants.

During each RS-tDCS session, once the stimulation has been activated the tDCS clinician will guide the participant in the word naming practice. Following the procedures of Henry et al. (2019), participants will be presented with photos of target items (via Zoom) and prompted to verbally produce the names of the pictures (common nouns and verbs) with the support of a word naming cueing hierarchy aimed at facilitating word retrieval through self-cueing³⁵. Participants will be guided as needed through the prompting of semantic, orthographic, and phonological information about the target word. All cues within the hierarchy will be presented to the participant for each item whether they correctly identify the stimulus or not. This is in effort to reinforce lexical retrieval of the target stimuli. The word naming approach is consistent across all participants in the study and described in detail below and outlined in Table 1.

- Semantic Self-Cue
 - When a target picture is presented for naming, the participant will first be instructed to generate semantic features/conceptual information using a fixed set of questions (e.g., “Where do you find it?” “What is it used for?”). At this stage, participants are also asked to provide any personal historical information about the target (e.g., “I drink this every morning”).
- Orthographic Self-Cue
 - Next, participants are asked about any orthographic (written) information they might have about the word (i.e., whether they can write the word or the first letter of the word).
- Phonemic Self-Cue

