8.1 Study Procedures

- Pre-screening:
 - Diagnosis of PPA and tDCS eligibility will be confirmed via medical records.

After subjects provide written informed consent, the following research procedures will take place over approximately 2 weeks:

- Baseline Visit:
 - Following procedures for our validated protocol^{37–41,43–47}, participants will first receive training on the use of the tDCS device and headset.
 - Participants will undergo a 90-second tDCS tolerability test to ensure the stimulation is tolerable. The participant will be given a one-time use code to initiate the stimulation, the tDCS device will

- ramp up to its target stimulation intensity (2.0mA) and after 90 seconds, participants will be instructed to press “0” to stop the test. Participants are free to stop the test at any time before the 90 seconds. Participants will then be instructed to remove the headset. Participants who cannot tolerate 2.0 mA will be considered a screen failure.
- Participants will complete self-report questionnaires about their language use and daily functioning through REDCap survey function (see assessments section 8.2 below).
 - Participants will identify a list of high frequency common nouns and verbs that they use in their daily life. This list of words will then be utilized to make the trained and untrained stimuli lists.
 - For exploratory research, participants will complete cognitive measures (QAB, BNT, COWAT).
 - tDCS Session 1:
 - Participants will have their first 30-minute remote session of 2.0mA active tDCS combined with word naming practice. Participants will be presented with the list of common nouns and verbs previously identified and practice verbally identifying those words from pictures with the help of a lexica retrieval cuing hierarchy. At each treatment session, participants will complete brief adverse event reports before and after each session. Once the study technician visually confirms correct headset placement and participants confirms adequate contact quality (moderate or good), the technician will provide the participant with a one-time use unlock code to enter into their tDCS device. The participant enters the code when ready to initiate the stimulation. During each stimulation session participants will listen to a guided mindfulness meditation audio track on the study provided laptop computer.
 - Remotely-Supervised tDCS Sessions 2-20:

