10.3 Sample Size Determination

The primary objectives of this study are to: 1) establish feasibility of an RS-tDCS and word naming practice in an adult PPA population, and 2) collect preliminary efficacy data to inform a grant application and sample size calculations for a large controlled trial.

A total of 30 adult PPA participants will be enrolled in the study based on the estimated number of eligible patient contacts across the study period.

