10.4 Description of Statistical Methods

For Objective 1, feasibility, individuals will be categorized as “compliant” based on percentage of study completion. Compliance with the interventions will be assessed by summarizing the distributions of numbers and proportions of

completed sessions. Descriptive analyses will be completed to identify any trends in predicting those participants who are most likely to be compliant (e.g., age, gender, baseline function).

For Objective 2, preliminary efficacy, we will convert performance at baseline and study end across study measures (QAB, BNT, COWAT, self-report questionnaires). Change in scores, indicating change following intervention, will be calculated for each compliant participant (defined as above). Descriptive analyses will be completed to identify any trends in predicting those participants who are most likely to have improvement in language function at study end (e.g., age, gender, baseline function) as well as corresponding degree of use of the RS-tDCS and word naming practice with magnitude of benefit.

11 Source Documents and Access to Source Data/Documents

Source data is all information, original records of clinical findings, observations, or other activities in a clinical trial necessary for the reconstruction and evaluation of the trial. Source data are contained in source documents. Examples of these original documents, and data records include: hospital records, clinical and office charts, laboratory notes, memoranda, subjects' diaries or evaluation checklists, recorded data from automated instruments, copies or transcriptions certified after verification as being accurate and complete, and subject files. It is acceptable to use CRFs as source documents. If this is the case, it should be stated in this section what data will be collected on CRFs and what data will be collected from other sources.

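### The untrained words are named as the control list and tested before and after treatment, but no stated analysis uses them as a control

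*Combined protocol and SAP*

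**What the plan says.** **Lists.** Under section 7.1.1 participants "will select 100 treatment items of personal relevance (i.e., high familiarity and frequency) from a fixed list of 220 possible items". The section continues: "Unselected items from the original list of 220 items served as the control word naming list". That leaves 220 − 100 = 120 untrained items. Section 8.1 (Baseline Visit) describes the lists differently. There the participant identifies common words, and "This list of words will then be utilized to make the trained and untrained stimuli lists".

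**Endpoints.** The Protocol Summary has a secondary endpoint, "The number of trained and untrained language probes identified at treatment end". This is a count at one time, with neither a change nor a contrast. Section 4.2.2 lists QAB, BNT, COWAT and the questionnaires, and omits the word lists.

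**Analysis.** Section 10.2 states that "pre- and post- language assessment outcomes (trained and untrained words, QAB, BNT, COWAT) will be compared", with the aim of finding out whether the intervention produced improvement. Section 10.4 says for Objective 2 that "we will convert performance at baseline and study end across study measures (QAB, BNT, COWAT, self-report questionnaires"; both word lists are absent. It calculates change for compliant participants.

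**Design.** The methodology is "Open Label Design" and everyone receives active stimulation with naming practice. The Schedule of Events shows one language assessment at baseline and one at treatment end. Under section 10.3 the 30 participants are "enrolled in the study based on the estimated number of eligible patient contacts". No effect size, SD, alpha or power is given.

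**The concern.** The plan builds a within-participant comparator and then gives it no comparative role. Trained and untrained words appear in 10.2 as two more pre-post outcomes beside QAB, BNT and COWAT.

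Section 10.2 sets a causal question. With no sham arm, no untreated arm and no repeated baseline, the untrained list is the only internal reference for word naming. A trained-word change taken alone combines item-specific learning with whatever moves both lists: a second exposure to the test, growing ease with the clinician and the video setting, and disease progression. A shared gain would be read as benefit. A shared decline could hide a real item-specific gain, which matters where section 2.1 gives preservation of language as the treatment goal.

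Sections 3.2 and 10.3 say the results will inform the power and sample size of a later trial, so an inflated or masked effect would be carried forward.

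**Working it through.** **1. The plan's own figure.** N = 30 rests on expected patient contacts, so there is no calculation to reproduce. No test or alpha is stated for the language outcomes. Everything below is illustrative and assumes a paired t-test at two-sided 0.05, n = 30, critical t (29 df) = 2.045, with changes in percentage points correct.

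**2. Shared gain, no training effect.** Let change on each list = g + S + L. S is shared by a participant's two lists (assumed SD 6) and L is specific to each list (assumed SD 4).

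- Trained pre-post change: SD = √(6² + 4²) = 7.21; SE = 7.21/√30 = 1.32.
- Trained minus untrained: g and S cancel; SD = √(2 × 4²) = 5.66; SE = 5.66/√30 = 1.03.

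| Shared gain g | g / 1.32 | Trained-word improvement nominally significant | Contrast, same direction |
|---|---|---|---|
| 0 | 0 | 2.5% | 2.5% |
| 2 | 1.52 | 31% | 2.5% |
| 3 | 2.28 | 60% | 2.5% |
| 5 | 3.80 | 96% | 2.5% |

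The third column is the noncentral-t probability. The last column holds by construction, because both lists were given the same gain.

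**3. Other SDs.** With a total SD of change of 8 or 10, the trained-word figures are 26% or 18% at 2 points, 51% or 36% at 3 points, and 91% or 75% at 5 points.

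**4. Precision.** The contrast gains or loses precision according to which variation dominates.

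- Shared SD 8, list SD 4: SE goes from √80/√30 = 1.63 to √32/√30 = 1.03.
- Shared SD 4, list SD 8: SE goes from √80/√30 = 1.63 to √128/√30 = 2.07.

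The 95% CI half-width is 2.045/√30 = 0.373 SD of the contrast: 1.9, 3.7 or 5.6 points for an assumed SD of 5, 10 or 15. A descriptive estimate needs no change in N.

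**5. Unequal baselines.** Trained items are chosen for familiarity, so they may start higher. Give both lists the same gain of 0.4 on the logit scale and no training effect; then gain = expit(logit p + 0.4) − p.

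| Baseline trained / untrained | Gain trained | Gain untrained | Contrast |
|---|---|---|---|
| 60% / 60% | 9.1 | 9.1 | 0.0 |
| 70% / 50% | 7.7 | 9.9 | −2.2 |
| 80% / 50% | 5.6 | 9.9 | −4.2 |

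With the SE of 1.03 from step 2, the last two rows lie 2.19/1.03 = 2.1 and 4.22/1.03 = 4.1 standard errors below zero. The raw contrast would then be nominally significant in the wrong direction in about 53% and 98% of trials. On the logit scale the list-by-time difference is 0.4 − 0.4 = 0, so the method used for baseline accuracy matters as much as the contrast itself.

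**The case against.** **The untrained words are not ignored.** A reader might infer that they are collected and never used. The documents do not support that: 10.2 gives them a pre-post comparison and the Protocol Summary counts them as an endpoint. With both changes reported, a reader could compare them by eye. What is missing is a stated contrast with an interval.

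**The list is not a clean control.** A reader might also infer that subtraction would remove retest and expectation effects altogether. The lists are neither randomised nor matched, participants know which words they practised, and subtraction removes only what is equal across lists. Section 8.2.2 also describes naming of both lists with the cueing hierarchy, so untrained items may be cued at assessment. This objection stands, and step 5 shows how large the error could be.

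**The contrast is not the tDCS effect.** Stimulation accompanies every session and could affect both lists, and gains that generalise to untrained words would be subtracted. This also stands. It is a reason to report the contrast beside the separate changes. Making it the main word-naming analysis would be a preference, not something the documents require.

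**The outcome is exploratory.** The primary endpoint is session completion and no test is planned, so the 60% describes an analysis the plan does not specify. A later randomised trial comparing change between arms would need the SD of pre-post change, which the current plan supplies. This lowers the weight of the point but leaves the causal wording of 10.2 unsupported.

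**Conclusion.** The point holds in a limited form. A list called the control is assessed twice and given no control role: 10.2 compares time points within each outcome, and 10.4 and 4.2.2 leave both lists out. Trained-word pre-post change alone cannot answer the question that 10.2 poses.

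The size cannot be fixed from the documents, which give no SDs, retest gains, baseline accuracies or rate of decline. Under the assumptions of steps 2 and 3, a shared gain of 3 points yields a spurious nominal improvement in about 36% to 60% of trials. The 2.5% for the contrast depends on equal gains in both lists and should not be quoted without that condition.

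Sections 7.1.1 and 8.1 disagree on whether untrained words come from the unselected items or from the words the participant identified. Until they are reconciled, the meaning of the contrast is not settled. Severity is modest because the primary endpoint is feasibility.

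**What to change.** 1. Add the trained and untrained word lists to sections 4.2.2 and 10.4.
2. Add to 10.2 and 10.4 an exploratory within-person contrast: change in percent correct on trained words minus change in percent correct on untrained words, with a 95% confidence interval. Percent correct is needed because 7.1.1 implies lists of 100 and 120 items. Report it beside the two separate pre-post changes.
3. State how baseline accuracy is handled. One option is an item-level logistic mixed model with a list-by-time interaction. Another is a comparison restricted to items matched on baseline naming, although matching on a single baseline is exposed to regression to the mean.
4. Reconcile 7.1.1 and 8.1 into one rule for building the untrained list, and state whether scored responses at assessment are cued or uncued.
5. State whether the contrast uses all participants with data or only the compliant participants of 10.4.
6. State its limits: it estimates item-specific practice gain under tDCS, does not isolate tDCS, removes expectation only as far as it is equal across lists, and shrinks if gains generalise to untrained words.

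The cost is a few sentences and a short analysis of naming data the plan already intends to collect, with no change in N. The list-building rule needs a protocol decision as well as analysis wording. The contrast may be less precise than the simple change if list-specific variation dominates (SE 2.07 against 1.63 in step 4).
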